This proposal is significant because the approach is novel, innovative and promising. The findings of this study will be the first step towards development of a reliable and effective treatment for POT. In addition, the TMS related physiology will shed further insights into the pathophysiology of POT and the mechanisms underlying treatment response.

GOAL AND SPECIFIC AIMS:

The **primary goal** of this study is to test the efficacy of low frequency rTMS therapy in POT. In this one year application, we expect to enroll twenty POT patients using a double blind randomized placebo controlled crossover design. We will enroll POT patients from our large research database (IRB approved protocol 416-2002) in addition to screening outpatient clinics. We plan to obtain IRB approval over the next few months while the grant is undergoing review process. Once the study is initiated, we will collect the data over the first six months. We will then plan for data analysis and publication over the subsequent six months. We believe the pilot findings from this study will be used for development of a larger multicenter clinical trial.

The **specific aims** of the proposal are:

Aim 1: To determine the clinical impact of 1-Hz rTMS therapy in POT when delivered to the cerebellum. This impact will be evaluated by the clinical scoring of leg tremors in standing posture, and the functional assessment of gait mobility. Comparisons will be drawn between T0 (before rTMS therapy), T1 (immediately or +5 minutes after) and T2 (60+ minutes after) assessments to determine the time course of effects.

Hypothesis: 1-Hz rTMS therapy will result in clinical improvement of leg tremors and gait mobility in POT. In addition improvement in scores at T1 assessment will be greater than those recorded at T2 assessment.

Aim 2: To determine the physiological effects of 1-Hz rTMS therapy in POT when delivered to the cerebellum.

Aim 2a: We will determine the effects on the amplitude and frequency of tremors recorded with surface EMG. Comparisons will be drawn between T0, T1 and T2 assessments. **Hypothesis:** 1-Hz rTMS therapy will reduce the amplitude of tremors and will have no effects on the frequency of tremors. The amplitude reduction in tremors will be greater at T1 assessment than at T2 assessment.

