Although the physician administering TMS will be aware of the status of the subject in terms of TMS versus sham-TMS, this physician will play no role in any of the outcome measures, and will not be present during any of the outcome assessments. Similarly, the investigators who perform the outcome measures will not be present during any of the TMS sessions, and therefore will remain blinded to the status of the patients with respect to TMS versus sham-TMS.

[figure not shown]
Video assessment: For the outcome assessment, we will videotape the items on TRS, the TUG test and 10 m walk test. These videos will be scored by blinded rater. We will obtain consent to obtain videos of all patients. Videos of clinical exam will be scored by blinded rater before therapy (T0), immediately after (T1) and 60+ minutes after (T2) therapy in each of the rTMS sessions. Subjects will be given three options as to how they would like their videos to be used.

Physiological assessments:

Tremor electrophysiology: POT tremors will be recorded on the surface EMG for amplitude and power spectral frequency analysis. We will use Bagnoli EMG system and Trigno wireless EMG system to record the surface EMG signals arising from muscles and the accelerometer findings respectively. The muscles involved in tremors and tremor like movements will be identified in each individual for the EMG recordings. The surface electromyography (EMG) signal is a minute electrical signal that emanates from contracting muscles. Trigno wireless system has sensors that use patented parallel-bar technology. This technology guarantees high fidelity signals to be recorded. Each sensor has a multi-function design and therefore along with recording of surface EMG signal, it embeds triaxial accelerometer. The accelerometer is judiciously mounted in the sensor so that the inertial behavior of the sensor remains intuitive. Accelerometer calibration is easily performed by carefully orienting the sensor with respect to the earth's gravitational field. This process creates a selective displacement of 1 g (i.e. 9.8m/s²), which conveniently allows the software to scale the sensor outputs accordingly. Accelerometers have a range of ± 1.5 or ± 6 g, selectable by software. Tremor amplitude and frequencies will be calculated with the surface EMG using Bagnoli system and accelerometry recorded using Trigno system. These tremor assessments will be done at T0, T1 and T2 rTMS therapy.

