Statistical analysis: The primary outcome measures in this study are change in total TRS score, leg tremor score, TUG test speed, 10m walk test time. The secondary outcome measures are amplitude and frequency of tremors on the surface EMG and the CBI recorded. Data will be presented as mean (SD) unless otherwise indicated. Each dependent measure will be examined using the following statistical approach. For each of the outcome variables, we will conduct a mixed model analysis using time and stimulation arm as repeated factors adjusted for baseline values, and subjects as the random factor. The model will include 2 within-subject factors: treatment (2 levels: active vs sham) and time (3 levels: T0, T1, and T2). If the interaction effects between stimulation arm and time are non-significant, they will be dropped. In case of significant main effects, post hoc pairwise comparisons will be corrected using Fisher least significant difference procedure in accordance with the closed test principle; i.e., post hoc comparisons will be declared non-significant if the global *p* value of the main effect (testing equality of all 2 stimulation arms simultaneously) are non-significant, but will be carried out without further correction in case of a significant global main effect. SPSS version 15.0 for Windows will be used for statistical computations. The 2-tailed significance level will be set at 0.05

The University of Florida nor the Principal Investigator hold a patent or license for any material, object or process used in this study. There is no license pending or under consideration or is there any intention to file a patent application at a later date.

Computer-based files will only be made available to personnel involved in the study through the use of access privileges, passwords and encryption. Passwords and encryption are used to ensure that the electronic data is secure and housed in a locked room.

Videos are edited in a secure research lab then the edited videos are deposited into a secured server in the University of Florida Health Science Center server. Access to the server and the videos on its restricted drive are limited to a directory group who need access to the movement disorders clinic or research videos on it

Data Safety Monitoring Plan

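### Masking of the video rater to time point and session, and the order in which clips are scored, are not specified, which leaves within-session time comparisons of the video-rated TRS items open to rater expectation

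*Combined protocol and SAP*

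**What the plan says.** The Video assessment paragraph has the TRS items, the TUG and the 10 m walk videotaped. It says "These videos will be scored by blinded rater", and then: "Videos of clinical exam will be scored by blinded rater before therapy (T0), immediately after (T1) and 60+ minutes after (T2) therapy". With two sessions, that makes six sets of clips per subject. The paragraph does not say what the rater is blinded to, and it does not mention coding, shuffling or removal of time labels. The data-security text after the Statistical analysis section has videos edited and kept on a restricted server, but it mentions no masking either.

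The one sentence that gives blinding any content stands just before the Video assessment paragraph. It concerns the investigators who perform the outcome measures. They stay away from the stimulation sessions and "therefore will remain blinded to the status of the patients with respect to TMS versus sham-TMS".

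Time matters to the stated aims. Aim 1 says: "Comparisons will be drawn between T0 (before rTMS therapy), T1 (immediately or +5 minutes after) and T2 (60+ minutes after) assessments". Its hypothesis fixes a direction: "In addition improvement in scores at T1 assessment will be greater than those recorded at T2 assessment". The Statistical analysis section fits arm (two levels) and time (three levels) as within-subject factors. On the interaction it says: "If the interaction effects between stimulation arm and time are non-significant, they will be dropped". Significant main effects are followed by pairwise comparisons without further correction. The global test that opens this step is described as "testing equality of all 2 stimulation arms simultaneously".

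**The concern.** Blinding to arm protects comparisons between arms. It does not protect comparisons between time points, because a rater who knows that a clip was taken just after stimulation may expect benefit whichever session it came from. Such a shift would be the same in real and sham sessions. It would therefore leave the arm and arm-by-time tests alone and appear as a time effect.

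This plan gives time effects a role. Aim 1 is worded as a comparison of T0, T1 and T2 and names no sham contrast, and its predicted pattern is the one that expectation would favour. If the interaction is dropped, time becomes a main effect averaged over real and sham, where an equal shift does not cancel.

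Two of the four primary outcomes, total TRS and leg tremor score, contain items rated 0 to 4 by judgement. The Clinical assessments section itself cites an inter-rater kappa of 0.10 to 0.65 for this scale. At stake is whether a reported improvement from T0 to T1 on these outcomes could be partly or wholly an artefact of scoring.

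**Working it through.** The plan gives no effect size, SD or power, so there is no figure of its own to reproduce. From the documents come n = 20, the crossover with two sessions, three time points and two-sided alpha 0.05. The size of the rater shift, the SD of change and the correlation between sessions are assumptions. Both checks assume no true effect, a rater who knows the time point, and the same shift in real and sham sessions.

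**Check 1: T0-T1 change averaged over the two sessions (paired t-test, 19 df, no gate).** Let s be the shift in points on the 0-4 leg item, SD the standard deviation of one within-session change, and r the correlation between a subject's changes in the two sessions.

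- SD of the averaged change = SD × √((1 + r)/2)
- dz = s / (SD of the averaged change)
- noncentrality = dz × √20, compared with the critical t of 2.093

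Example with s = 0.25, SD = 0.7, r = 0: 0.7 × √0.5 = 0.495; dz = 0.25/0.495 = 0.505; noncentrality = 0.505 × 4.472 = 2.26; rejection probability 57.3%.

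| Shift | SD | r = 0: dz | r = 0: false rate | r = 0.5: dz | r = 0.5: false rate |
|---|---|---|---|---|---|
| 0.15 | 1.0 | 0.212 | 14.7% | 0.173 | 11.4% |
| 0.15 | 0.7 | 0.303 | 25.1% | 0.247 | 18.3% |
| 0.25 | 1.0 | 0.354 | 32.4% | 0.289 | 23.2% |
| 0.25 | 0.7 | 0.505 | 57.3% | 0.412 | 41.7% |

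At r = 0.7 the range is about 11% to 38%. Positive correlation is plausible for two sessions in the same person, so the r = 0 column is the high end.

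**Check 2: which tests are affected.** A 2 × 3 within-subject ANOVA was simulated with 4,000 runs per setting. The bias is b at T1 and b/2 at T2, with b in SDs of one T1-T0 change. The variance components are assumed.

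| b | Time main effect | Arm × time | Arm |
|---|---|---|---|
| 0 | 0.055 | 0.053 | 0.051 |
| 0.2 | 0.188 | 0.050 | 0.049 |
| 0.3 | 0.362 | 0.044 | 0.051 |
| 0.5 | 0.774 | 0.051 | 0.056 |
| 0.8 | 0.996 | 0.048 | 0.050 |

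The bias goes entirely into the time test. The two tests that compare real with sham stay near 5% at every b. The row b = 0 is what masking to time point would restore, as far as this source of bias goes.

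**The case against.** The strongest objection is that the documents are silent rather than wrong. A reader might infer that the rater is shown the time point, because scoring is listed by T0, T1 and T2. The sentence does not say so: it lists the assessments to be scored, and nothing says that labels reach the rater. The sentence limiting blinding to real versus sham concerns the investigators who perform the outcome measures and does not define the video rater's masking. This stands. The supportable statement is that masking to time point is not specified.

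Second, a reader might infer that the trial's efficacy result is compromised. It is not, as long as the rater is blind to arm. Every subject has a sham session scored the same way, and an equal shift cancels in the arm and arm-by-time tests. A time effect of equal size in both arms is in any case no evidence that rTMS works. This stands too.

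Third, the gate for pairwise tests is described as a test of the two arms. Read literally, with no treatment effect it would block the T0-T1 pair about 95% of the time. This stands in part. Two arms leave nothing for pairwise follow-up to add, time is the only factor with several pairs, and the overall time test is not itself behind that gate. The wording leaves both readings open.

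Fourth, exposure is limited. TUG and the 10 m walk are timed, TRS Part C is reported by the patient, and EMG and CBI are not rated from video. This stands, and the point is confined to the video-rated TRS items.

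**Conclusion.** The point holds as a gap in specification with a limited consequence. The plan does not say that clips are masked to time point and session or scored in a concealed order. Aim 1 and the rule for dropping the interaction leave room for conclusions drawn from time alone. If the rater can tell the time point, within-session comparisons of total TRS and leg tremor score can be biased towards the predicted pattern.

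The size is illustrative. The 15% to 57% range, or about 11% to 42% at correlation 0.5, rests on an assumed shift and SD, on a rater who knows the time point, and on an ungated paired test in place of the planned mixed model. A reader might take it as the plan's false-positive rate. The documents do not support that, since they supply neither the shift nor the SD and do not say what the rater knows.

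The point matters moderately if conclusions rest on time effects. It is minor if they rest on the arm-by-time contrasts. The change is worth making because it costs little and removes an avoidable source of bias from two primary outcomes.

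**What to change.** In the Video assessment paragraph, state that each subject's six clips (two sessions by three time points) are stripped of date and time, given random codes, shuffled, and scored in one batch by the same rater, masked to arm, session and time point. Staff who already edit and store the videos can do the coding. The cost is some file handling and a delay, because scoring must wait until both sessions are complete.

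Masking does not remove practice, fatigue or placebo effects over time, and these produce a time pattern even with a fully masked rater. The Statistical analysis section should therefore state that the efficacy conclusion for Aim 1 rests on the real-minus-sham change from T0 at T1 and at T2, with the interaction kept in the model for that purpose, and not on a time main effect. This requires only a wording change and no further data.

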Data Analysis: The EMG signal will be amplified (gain = 1000) and band pass- filtered between 20 and 450 Hz (Delsys, Boston, MA, USA) for the Bagnoli amplifier and analyzed. For analysis, the data will be digitized with 12-bit resolution by a 1401-plus (CED, Cambridge, UK) analogue-to-digital converter and digitally full-wave rectified. Sampling will be performed at 512 Hz. However, since each burst occurs at only 4-12 Hz or slower, the envelope of each burst will be the feature of interest in this study. The signals will be displayed and stored on computer disc by a software package (CED Spike 2) running on microsoft windows computer. We will use fast Fourier transform to generate auto spectra. For frequency of the tremors, the mean (\pm standard deviation) frequency of the 4-12-Hz range EMG spectral peak will be averaged over all muscles and over all trials recorded for each subject. The values will be estimated from the power spectra to the nearest 0.25 Hz. For amplitude of the tremors, the y-axis of the spectral plots will be used which represent the root-mean-square power.

TMS measure: We will record cerebellar inhibition (CBI) that is a well-established TMS measure.^{23,24} A paired pulse protocol will be used with right cerebellar stimulation as the conditioning stimulus,

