(cerebellar conditioning stimulus or CCS) and left motor cortex stimulation (M1) as the test stimulus (TS). We will determine the 'TS 0.5mV' which will indicate a stimulator setting (determined to the nearest 1% of the maximum stimulator output) that produces a peak-to-peak MEP amplitude of $\geq 0.5\text{mV}$ in at least five out of 10 trials. Interstimulus intervals (ISI) of 3 to 8 milliseconds at increment of 1 millisecond will be tested. Each run will consist of 10 trials of each of the paired stimuli (CCS-TS) and 10 trials of TS alone delivered in random order (70 trials in total). Inhibition trial will be expressed as a ratio of mean conditioned to mean unconditioned MEP amplitude for each subject. The intensity for cerebellar stimulation will be set at 5% of the stimulator output below the active motor threshold. Active motor threshold is the minimum intensity required to elicit MEPs of more than $50\text{ }\mu\text{V}$ above the background EMG. The cerebellar coil will be a double cone coil attached to MAGSTIM machine (Magstim Company, Dyfed, UK) positioned 3 cm lateral to the inion on the line joining the inion and the external auditory meatus. This coil position and current direction have been found to be optimal for suppressing the contralateral motor cortex. The second coil will be a flat figure-of-eight coil (70 mm mean diameter) placed on the left motor cortex. An optimal position for eliciting MEPs from the right first dorsal interosseous FDI muscle will be identified. The handle of the coil will be pointed backwards and perpendicular to the presumed direction of the central sulcus, about 45° to the midsagittal line. The direction of the induced current is from posterior to anterior, optimal to activate the motor cortex trans-synaptically. Surface EMG will be recorded from the right first dorsal interosseous (FDI) muscle with disposable silver-silver chloride disc electrodes in a tendon-belly arrangement. The signal will be filtered (band pass 2 Hz to 2.5 kHz), amplified, digitized at 5 kHz and stored on a laboratory computer for offline analysis.

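### The tremor EMG is sampled at 512 Hz although its 20-450 Hz pass band needs more than 900 Hz; the likely cost is a modest loss of precision in secondary outcomes.

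*Combined protocol and SAP*

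**What the plan says.** The Data Analysis paragraph under Physiological assessments sets out the tremor EMG chain. The Bagnoli signal is amplified and "band pass- filtered between 20 and 450 Hz". It then passes through an "analogue-to-digital converter and digitally full-wave rectified", and "Sampling will be performed at 512 Hz". No further anti-alias filter is described.

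The next sentence adds that "the envelope of each burst will be the feature of interest in this study". Tremor frequency is the "frequency of the 4-12-Hz range EMG spectral peak", averaged over muscles and trials; "The values will be estimated from the power spectra to the nearest 0.25 Hz". For amplitude, "the y-axis of the spectral plots will be used which represent the root-mean-square power".

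The TMS measure section describes the plan's other EMG recording, from the hand muscle. Its upper band edge is 2.5 kHz and it is "digitized at 5 kHz and stored on a laboratory computer for offline analysis".

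The Statistical analysis section lists EMG amplitude and frequency as secondary outcomes. Aim 2a predicts a lower amplitude, more so at T1 than at T2, and an unchanged frequency.

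**The concern.** A signal carrying content up to 450 Hz cannot be represented faithfully at 512 samples per second: everything between 256 and 450 Hz folds to lower frequencies. By the stated order of steps this happens before rectification, so the envelope is formed from an undersampled signal. The hand-muscle recording is digitised at twice its upper edge, so the shortfall is specific to the tremor EMG.

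At stake is the precision of the two EMG outcomes in Aim 2a. A raised noise floor matters most where the tremor peak is smallest. It could make a strongly suppressed tremor look slightly larger and its frequency less certain. Content folded at acquisition cannot be separated afterwards.

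**Working it through.** **Inputs from the plan.** Upper band edge 450 Hz, lower edge 20 Hz, rate 512 Hz, rectification after digitisation, peak read between 4 and 12 Hz to the nearest 0.25 Hz. The plan states no required rate, so there is no figure of its own to reproduce.

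**Arithmetic.**
- Rate needed: more than 2 × 450 = 900 Hz. The stated rate is 512/900 = 57% of that.
- Highest frequency represented at 512 Hz: 512/2 = 256 Hz.
- Part of the pass band that folds: (450 − 256)/(450 − 20) = 194/430 = 45% by width.
- Where it lands: 512 − 256 = 256 Hz down to 512 − 450 = 62 Hz. That is outside both the 4-12 Hz window and the 13-18 Hz disease band.
- Hand-muscle EMG: 5 kHz / 2.5 kHz = 2, nominally at the limit.

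**Simulation at 8 Hz.** Gaussian noise band-limited to 20-450 Hz was modulated at 8 Hz, sampled, rectified and transformed with 4 s windows (0.25 Hz bins), and the peak was taken in 4-12 Hz. There were 1200 records per cell. Not in the documents, hence assumed: the share of EMG power above 256 Hz (6%, 16%, or 45% for a flat spectrum), modulation depth (0.5 to 0.05) and record length (10 s or 30 s).

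Noise-floor power at 512 Hz divided by that at 1024 Hz was about 1.09, 1.35 and 1.93 for the three spectra. Square roots give RMS factors of 1.04, 1.16 and 1.39.

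RMS peak height at 512 Hz relative to 1024 Hz, over all spectra and both record lengths:
- depth 0.5: higher by 0.0-0.2%
- depth 0.2: higher by 0.2-1.0%
- depth 0.1: higher by 0.7-3.9%
- depth 0.05: higher by 1.6-11.8%

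No record had its peak misread by more than 0.25 Hz at depth 0.2 or above. At depth 0.1 misreads were 0% for 30 s records; for 10 s records they were 0.8-2.8% at 512 Hz and 0-2.0% at 1024 Hz. Misreads at depth 0.05:

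| Record | Power above 256 Hz | 512 Hz | 512 Hz with 250 Hz low-pass | 1024 Hz |
|---|---|---|---|---|
| 10 s | 6% | 58.3% | 59.8% | 53.2% |
| 10 s | 16% | 47.6% | 50.7% | 34.6% |
| 10 s | 45% | 49.6% | 46.8% | 15.5% |
| 30 s | 6% | 19.4% | 23.9% | 15.1% |
| 30 s | 16% | 9.6% | 14.9% | 2.9% |
| 30 s | 45% | 11.2% | 12.0% | 0.4% |

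The Monte Carlo standard error is at most √(0.5 × 0.5/1200) = 1.4 percentage points. Mean frequency bias at 512 Hz never exceeded 0.06 Hz.

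**Simulation at 15.5 Hz, inside the disease band, 512 against 2048 Hz.** Floor power was about 5-8% higher when 4-6% of EMG power lay above 256 Hz, and about 100% higher for a flat spectrum. Peak height changed by under 1% at depth 0.3 or more. At depth 0.05 with 10 s records, the flat spectrum gave misreads of 41% against 13% (4% against 0% at 30 s). The two spectra with 4-6% above 256 Hz gave 39% against 39% and 42% against 45%, so no worsening.

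**The case against.** The strongest case on the other side is that the plan analyses the burst envelope, not the raw EMG spectrum. Sampling keeps the size of each sample, so the rectified envelope and a clear tremor peak survive. A reader might infer that folding puts false energy on the tremor frequency. It does not: the folded content lands at 62-256 Hz. Removing it with a 250 Hz low-pass while keeping 512 Hz leaves misreads about the same. The loss comes instead from having too few independent samples of the rectified signal.

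A reader might also infer that the low rate could hide a strong treatment effect. The figures do not bear that out. When modulation depth was cut from 0.6 to 0.05 (1 − 0.05/0.6 = 92% suppression) on 10 s records, the measured amplitude reduction was 88.5% at 512 Hz against 90.4% at 2048 Hz for a flat spectrum. With 7% of power above 256 Hz it was 88.1% against 88.5%.

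Nor do the documents support expecting a third to a half of frequencies to be misread. That needs near-abolition of tremor and short records. At low shares of power above 256 Hz, most such misreads occur at an adequate rate too. Aim 2a predicts a reduction, not near-abolition. The plan also averages frequency over muscles and trials: with 12 records averaged (an assumed number), no 30 s mean was off by more than 0.5 Hz. For 10 s records at depth 0.05 the rates were 4% against 0% (flat) and 16% against 8% (7% share), from only 25 means per cell. Tremor is also measured by accelerometry, to which this EMG filter setting does not apply.

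All of this limits the size of the problem. None of it makes 512 Hz adequate for a 450 Hz band, and the accelerometer does not repair the EMG outcomes.

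**Conclusion.** The inconsistency is real and follows from the plan's own two figures. Its consequence is minor: a higher noise floor and, under narrow conditions, slightly inflated amplitude and a more scattered peak frequency. Both conditions must hold: tremor nearly abolished (modulation depth around 0.1 or below in these runs) and appreciable EMG power above 256 Hz. The documents give neither the EMG spectrum nor the record length nor the residual modulation, so the size can only be stated as a range. Only secondary outcomes are involved; the clinical primary outcomes are untouched.

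One ambiguity remains. If 512 Hz is meant as a resampling rate after faster digitisation and rectification, the folding argument would have to be restated. The text does not say so.

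**What to change.** In the Data Analysis paragraph, change the tremor-EMG sampling rate to above 900 Hz, for example 1000-2000 Hz, then rectify and compute the spectrum. The cost is an acquisition setting and larger files; the plan already digitises its hand-muscle EMG at 5 kHz.

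Lowering the upper filter edge below 256 Hz while keeping 512 Hz is not a substitute. It stops the raw EMG from folding but does not recover precision, as the low-pass column above shows.

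If 512 Hz is a resampling rate, state the digitisation rate, say that rectification comes before resampling, and name the filter applied before resampling.

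Separately, the 4-12 Hz search window in the same paragraph conflicts with the 13-18 Hz tremor given in Background and Significance and in Study design. A tremor in that band lies outside the window at any sampling rate, so those passages must be reconciled in their own right.

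### Aim 2b rests on the CBI ratio alone: the test-alone MEP is recorded but not analysed, so a ratio change cannot be securely attributed to cerebellar inhibition

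*Combined protocol and SAP*

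**What the plan says.** The TMS measure section describes a paired-pulse protocol. A conditioning pulse over the right cerebellum precedes a test pulse over the left motor cortex, and the result is summarised as follows: "Inhibition trial will be expressed as a ratio of mean conditioned to mean unconditioned MEP amplitude for each subject". Six intervals are used: "Interstimulus intervals (ISI) of 3 to 8 milliseconds at increment of 1 millisecond will be tested". Each run has ten paired trials per interval and ten test-alone trials, 70 in all.

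Test intensity is set by a response criterion: "We will determine the 'TS 0.5mV' which will indicate a stimulator setting" at which the MEP reaches 0.5 mV or more in at least half of ten trials. For the conditioning pulse, "The intensity for cerebellar stimulation will be set at 5% of the stimulator output below the active motor threshold". Neither statement says whether the setting is kept from T0 or determined again at T1 and T2.

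The schedule of assessments places CBI at T0, T1 and T2 on both days. In the Statistical analysis section, "The secondary outcome measures are amplitude and frequency of tremors on the surface EMG and the CBI recorded". Each outcome goes into a "mixed model analysis using time and stimulation arm as repeated factors adjusted for baseline values, and subjects as the random factor". The test-alone MEP is not listed as an outcome, covariate or check. Motor thresholds appear only as a means of setting intensities.

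**The concern.** Aim 2b hypothesises that 1-Hz rTMS normalises cerebello-cortical inhibition, and CBI is its only measure. A ratio of two MEPs depends on both. If real rTMS alters the size of the test MEP and the conditioned MEP does not scale with it, the ratio changes although the inhibitory input has not.

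Neither safeguard in the design removes such a shift. The sham coil is described as not stimulating the cortex, so a shift caused by real stimulation would occur only in the real session and pass into the active-sham contrast. Baseline adjustment does not help either, because the shift would arise after T0.

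At stake is the mechanistic reading. A ratio difference could be reported as a cerebellar effect when it reflects test size, or a real change in inhibition could be offset. The four primary clinical outcomes are not involved.

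**Working it through.** **Run length.** Intervals of 3, 4, 5, 6, 7 and 8 ms make six. 6 × 10 paired + 10 test-alone = 70, which matches the plan. The ratios at all six intervals therefore share one ten-trial denominator.

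**How tightly the 0.5 mV rule fixes test size.** Let p be the chance that a single trial reaches 0.5 mV at a given setting. The setting passes with probability P(X ≥ 5), where X is binomial (10, p). For p = 0.35, 0.50, 0.65 and 0.90 this is 0.25, 0.62, 0.91 and above 0.99. The rule is a floor: a setting well above the target also passes, so test size is only loosely standardised.

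**What a change in test size does to the ratio when inhibition is constant.** The documents give no MEP values, so everything here is assumed. The starting test MEP is U = 0.5 mV and the ratio is 0.60, so the conditioned MEP is C = 0.30 mV. There are three models:

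- Proportional: C = 0.60 × U. The ratio is always 0.60.
- Sigmoid with plateau M: MEP = M/(1 + exp(−s)), and conditioning lowers the drive s by a fixed amount. Equivalently, the odds MEP/(M − MEP) are multiplied by k = [0.3/(M − 0.3)] / [0.5/(M − 0.5)].
- Subtractive: C = U − 0.20.

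Sigmoid example with M = 1.5: k = (0.3/1.2)/(0.5/1.0) = 0.50. At U = 1.0 the odds are 1.0/0.5 = 2, the conditioned odds are 1, C = 0.75 and the ratio is 0.75.

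| Test MEP | Proportional | Sigmoid M = 1.5 | Sigmoid M = 3 | Sigmoid M = 5 | Subtractive |
|---|---|---|---|---|---|
| 0.30 mV (−40%) | 0.60 | 0.56 | 0.58 | 0.59 | 0.33 |
| 0.50 mV | 0.60 | 0.60 | 0.60 | 0.60 | 0.60 |
| 0.75 mV (+50%) | 0.60 | 0.67 | 0.63 | 0.61 | 0.73 |
| 1.00 mV (doubled) | 0.60 | 0.75 | 0.65 | 0.63 | 0.80 |

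A larger test MEP reads as weaker inhibition and a smaller one as stronger, except in the proportional case.

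**Masking.** Suppose inhibition strengthens so that the ratio at 0.5 mV would be 0.50. It still reads 0.60 if the test MEP rises by a factor of 1.67, 2.67 or 4.0 (sigmoid, M = 1.5, 3 or 5), or 1.25 (subtractive: 0.25/0.625 = 0.40, so the ratio is 0.60). Under the sigmoid, masking needs a large rise.

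**The case against.** Several stronger readings are tempting, and the documents do not support them.

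- A reader might infer that the plan itself shows rTMS at this site shifting motor-cortex output, from "This coil position and current direction have been found to be optimal for suppressing the contralateral motor cortex". That sentence concerns the double-cone conditioning coil and the paired-pulse effect. The rTMS is given at the same scalp point but with a different coil, and nothing is said about a lasting change in the test-alone MEP. A shift is possible, not documented.
- A reader might infer that test size is uncontrolled after rTMS. The plan is silent on re-setting, which is not the same. If the test stimulus is re-determined before every run, the drift largely disappears.
- A reader might count it as a defect that the ratio hides a proportional change in both MEPs. For Aim 2b that is what normalising is for, and motor-cortex excitability is not an aim.
- A reader might infer a high false-positive rate. Take a noncentral t on one active-sham contrast, with n = 20 and an assumed contrast SD of 0.2. A doubled test MEP gives a significant result in 89%, 20% or 9% of trials (plateau 1.5, 3 or 5 mV), and a 50% rise in 29%, 8% or 6%, against a nominal 5%. The 89% needs a doubling, the lowest plateau and no re-setting. The calculation is also not the planned mixed model, so none of these is an error rate of this plan.

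What survives is narrower. The ratio is the sole measure, the quantity that would reveal a test-size shift is recorded but unused, and neither sham nor baseline adjustment would remove such a shift. Even with re-setting, the change in stimulator setting would be the sign of altered excitability, and it is not analysed either.

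**Conclusion.** The point holds as a gap in interpretation, not as a demonstrated bias. With the ratio alone, Aim 2b cannot separate a change in cerebellar inhibition from a non-proportional change in test-MEP size.

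The size cannot be determined from the documents. Under the assumed sigmoid (plateau 1.5 to 5 mV, starting ratio 0.60 at 0.5 mV), the shift is 0.01 to 0.07 for a 50% rise in the test MEP and 0.03 to 0.15 for a doubling. It is zero if both MEPs scale together or if test size is held constant by re-setting. The subtractive model gives larger shifts, but the documents give no reason to prefer it.

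The consequence is confined to one secondary mechanistic outcome in a 20-patient pilot. It merits action because the remedy uses data the trial already collects.

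**What to change.** 1. Analyse log test-alone MEP amplitude in the same treatment-by-time mixed model as the other outcomes. Attribute a CBI difference to cerebellar inhibition only in light of that result. Report the active-sham estimate with its confidence interval, since a non-significant test in 20 patients does not show that test size was stable.
2. Add a sensitivity model of log conditioned MEP with log unconditioned MEP of the same run as covariate. The log ratio is the special case with slope fixed at 1. Do not regress the ratio on its own denominator, which builds in a mathematical coupling. State that the covariate is measured after treatment and is a ten-trial mean, so the adjustment is supportive only.
3. State whether the test-stimulus setting is fixed from T0 or re-set before each run, and say the same for the conditioning intensity. If the test stimulus is re-set, record the setting and analyse it by arm and time as the excitability measure, because the test-alone MEP will then have been held near target.

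The cost is SAP wording and one or two extra models on recorded data. Re-setting is not required for this fix; it would add pulses to a T1 slot that already holds the clinical tests, the EMG and a 70-trial CBI run.
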